8.8 Electrocardiograms

Electrocardiograms will be performed in triplicate and sent to a central reviewer. Subjects should be lying quietly in a fully supine position for at least 10 minutes prior to each 12-lead ECG. A 12-lead ECG will be performed at the Screening Visit, Day 1, Week 2, Week 4, Week 8, Week 12, and the ET Visit, if applicable.

The Investigator will assess ECG data as normal, abnormal not clinically significant, or abnormal clinically significant. Any clinically significant abnormalities should be documented as medical history/adverse event/SAE as applicable. All ECG traces will be kept as source data.

8.9 Physical Examinations

A full physical examination will be performed at the subject's first study visit, either at the Pre-Screening Visit, if applicable, or the Screening Visit, Week 12, and the ET Visit, if applicable. A full physical examination includes genitourinary examination per the Investigator's discretion and does not include a rectal examination.

A symptom-directed physical examination will be conducted at the Screening Visit (only for subjects who required a wash-out period and completed the full physical examination at the Pre-Screening Visit), Day 1, Week 2, Week 4, Week 8, and the Follow-up Visit (only for subjects who had an abnormal result at Week 12 [or the ET Visit, if applicable] or an ongoing treatment-related adverse event).

Height will be measured at the subject's first study visit, either at the Pre-Screening Visit, if applicable, or the Screening Visit and weight will be measured at all study visits, excluding the Follow-up Visit. BMI will be calculated at the Screening Visit.

8.10 Medical/Surgical History and Demographics

Medical and surgical history and demographics will be recorded at the Pre-Screening Visit, if applicable, and/or the Screening Visit. Subject eligibility will be evaluated to determine all inclusion and none of the exclusion criteria are met. The Investigator will inquire with the subject at Day 1 to determine if there have been any changes in the subject's health affecting eligibility or requiring an update to their medical and surgical history.

8.11 Reserve Samples

Reserve samples will be collected for the optional assay of exploratory biomarkers or pharmacokinetic assessments. Reserve blood samples will be collected at all study visits during the Treatment Period and the ET Visit, if applicable, to be available for analysis of exploratory biomarkers associated with lipid metabolism, repeat lipid testing, and/or repeat or additional clinical laboratory and urine testing in the event of a safety issue. The reserve samples collected on Visits 3 and 5 may be used for assay of plasma drug concentrations (PK Analysis). The PK concentration values be used to confirm subject compliance, summarize of observed plasma concentrations, or a model based population pharmacokinetic analysis.

9 STATISTICS

9.1 Sample Size

The primary efficacy endpoint is the percent change from baseline to Week 12 in LDL-C, with the primary focus on the overall set of randomized subjects. The efficacy within each baseline statin intensity (high-intensity; moderate-intensity) stratum is also of interest for this study; thus, the study is powered for the analyses within each baseline statin intensity stratum. A sample size of 26 randomized subjects in the gemcabene 600 mg group and 26 randomized subjects in the placebo group within each baseline statin intensity stratum is expected to provide 80% power to detect a difference of 17% in the percent change from baseline to Week 12 in LDL-C between the gemcabene treatment group and the placebo group within each baseline statin intensity stratum. This calculation is based on a 2-sided t-test at the 5% level of significance ($\alpha = 0.05$), a common standard deviation of 20, and a drop-out rate of 10%. The sample size of 26 randomized subjects in each baseline statin intensity stratum in the gemcabene 600 mg group gives a total of 52 randomized subjects in the gemcabene 600 mg group. Twenty-six randomized subjects in each baseline statin intensity stratum in the placebo group gives a total of 52 randomized subjects in the placebo group. Thus, the total study sample size is 104 randomized subjects.

There are no planned interim analyses in the study.

9.2 Analysis Populations

9.2.1 Full Analysis Set

The Full Analysis Set (FAS) will consist of all randomized subjects who receive at least 1 dose of study drug and have at least 1 post-baseline efficacy assessment. All efficacy analyses will be performed on the FAS.

9.2.2 Per Protocol Set

The Per Protocol Set (PPS) will include all FAS subjects who complete the 12-week Treatment Period without major protocol deviations. The PPS will be used to assess robustness of the analysis results. Protocol deviations will be reviewed and the PPS will be determined prior to treatment unblinding at the end of the study.

9.2.3 Safety Analysis Set

The Safety Analysis Set (SAS) will include all randomized subjects who receive at least 1 dose of study drug. All safety analyses will be conducted on the SAS.

9.3 Statistical Methods

9.3.1 Analysis of Efficacy

9.3.1.1 Primary efficacy analyses

The primary efficacy endpoint is the percent change in fasting LDL-C from baseline to Week 12. The primary efficacy endpoint will be analyzed using analysis of covariance (ANCOVA) with percent change from baseline to Week 12 in LDL-C as the dependent variable; treatment, baseline statin intensity (high-intensity; moderate-intensity), and baseline diabetes (yes or no) as factors; and baseline fasting LDL-C as a covariate. Baseline will be defined as the average of the LDL-C values at Screening/Visit S1 and pre-dose Day 1/Visit T1. The ANCOVA will be performed using the FAS, with subjects included in their randomized treatment group regardless of the treatment they actually received. Missing values for Week 12 will be imputed using last observation carried forward (LOCF); only post-baseline values will be used for the imputation. The least-squares mean (LSM) and standard error (SE) will be provided for both treatment groups, along with the placebo-corrected LSM, its 95% confidence interval (CI), and associated p-value. A 2-sided test with a significance level of 0.05 will be used for the comparison of gemcabene 600 mg to the placebo group. If non-normality is detected, then either the data will be transformed so that it is normally distributed or a nonparametric test will be used.

A confirmatory analysis of the primary efficacy endpoint will be performed using the PPS.

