The duration of the Treatment Period will be 12 weeks. Eligible subjects will be randomized via an interactive web/voice response system (IWRS/IVRS) on Day 1 in a 1:1 ratio to the following treatment groups: placebo or gemcabene 600 mg. Subjects will be stratified by statin intensity (as defined in Table 1) and Type 2 diabetes (yes or no). Subjects defined as diabetic will be those receiving concomitant anti-diabetic medication at screening. Randomization within a baseline statin intensity stratum will be capped at 52 subjects; once 52 subjects are randomized into a baseline statin intensity stratum, no further subjects in that statin intensity will be randomized (subjects in the other baseline statin intensity stratum will continue to be randomized until there are 52 randomized subjects in that stratum). By also stratifying on baseline diabetes

(yes, no), diabetic subjects will be evenly distributed across the treatment groups and statin-intensity subgroups. The first dose of study drug will be administered at the site on Day 1. On days with a scheduled office visit with blood sample collection, subjects will remain fasted (at least 10 hours) and should not take gemcabene until after the blood samples are collected. For days when the subject will self-dose, subjects will be instructed to take study drug at the same time in the morning with a full glass (8 ounces) of water either with or without food.

Post-randomization clinic visits will occur at Week 2, Week 4, Week 8 and Week 12. The Follow-up Visit will occur 4 weeks (± 3 days) after the last dose of study drug.

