4.3 Withdrawal Criteria

Participation of a subject in this clinical study may be discontinued for any of the following reasons:

- The subject withdraws consent or requests discontinuation from the study for any reason;
- Occurrence of any medical condition or circumstance that exposes the subject to substantial risk and/or does not allow the subject to adhere to the requirements of the protocol;
- Any SAE, clinically significant adverse event, severe laboratory abnormality, concomitant illness, or other medical condition which indicates to the Investigator that continued participation is not in the best interest of the subject;
- Pregnancy;
- Requirement of prohibited concomitant medication which is prohibited by the protocol;
- Subject failure to comply with protocol requirements or study-related procedures; or
- Termination of the study by the Sponsor or the regulatory authority.

If a subject withdraws prematurely from the study due to the above criteria or any other reason, study staff should make every effort to complete the full panel of assessments scheduled for the Early Termination (ET) Visit. The reason for subject withdrawal must be documented in the electronic Case Report Form (eCRF).

In the case of subjects lost to follow-up, attempts to contact the subject must be made and documented in the subject's medical records.

Withdrawn subjects will not be replaced. The sample size calculation accounts for a 10% dropout rate in the study.

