11 EFFICACY PARAMETERS

11.1 Primary Analysis

The primary efficacy endpoint (percent CFBL to Week 12 in LDL-C) will be analyzed using ANCOVA and the FAS population. The null hypothesis to be tested is that there is no difference in the expected percent CFBL to Week 12 in LDL-C between the active treatment (subjects treated with gemcabene 600 mg) and placebo (subjects treated with placebo) groups after adjusting for baseline statin-intensity stratum, baseline diabetes status, and baseline LDL-C. Explicitly, in the ANCOVA, percent CFBL to Week 12 in LDL-C will be the dependent variable whereas randomized treatment group (gemcabene 600 mg or placebo), baseline statin-intensity stratum (moderate or high), and baseline diabetes status (yes or no) will be included as factors, and baseline LDL-C will be included as a covariate. LOCF will be used to impute missing values for Week 12; only post-baseline values will be used for imputation. The least-squares mean (LSM) and standard error (SE) for percent CFBL to Week 12 in LDL-C for each treatment group and the least-squares mean and 95% confidence interval (CI) of the treatment difference will be produced from the model using type III sums of squares to estimate the magnitude of the treatment effect. The following SAS code will be used to conduct the ANCOVA:

```
proc glm data=data;  
  class Drug(ref="Placebo") Diabetes StatinStrat;  
  model pctCFBL = Drug Diabetes StatinStrat Base / solution;  
  lsmeans Drug / stderr pdiff out=adjmeans;  
run;
```

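### Missing Week 12 LDL-C is filled only by carrying on-treatment values forward, so gemcabene drop-outs keep their on-drug reduction and no planned analysis tests informative drop-out

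*Protocol*

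**What the plan says.** The primary analysis is an ANCOVA of percent change in LDL-C at Week 12 in the Full Analysis Set. Protocol 9.3.1.1 gives the missing-data rule: "Missing values for Week 12 will be imputed using last observation carried forward (LOCF); only post-baseline values will be used for the imputation". SAP 11.1 agrees: "LOCF will be used to impute missing values for Week 12; only post-baseline values will be used for imputation".

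Two other SAP sections are narrower. SAP 9.4 allows only on-treatment values to be carried forward. Its worked example replaces a Week 12 value taken more than 2 days after the last dose with the last on-treatment value. SAP 9.6 likewise disregards efficacy values later than 2 days after the last dose. SAP Section 8, which lists departures from the protocol, does not mention this restriction.

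The only other planned analysis of the primary endpoint repeats the ANCOVA in the Per Protocol Set (Protocol 9.3.1.1, SAP 11.1), which is limited to subjects who complete 12 weeks of treatment. For secondary endpoints, including Week 12 LDL-C within each statin stratum, SAP Section 8 drops the per-protocol repeat.

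Drop-out is expected. Protocol 4.3 says that withdrawn subjects are not replaced and that "The sample size calculation accounts for a 10% dropout rate in the study".

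**The concern.** Under SAP 9.4, a gemcabene subject who stops after Week 2, 4 or 8 enters the Week 12 analysis with an on-drug value, even if a later off-drug value was measured. If LDL-C rises again after stopping, the analysis credits that subject with a benefit no longer present at Week 12. The estimate then describes an effect while on drug. The Full Analysis Set and randomized-group wording invite the reader to take it as an effect in everyone randomized.

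The two rules can also give different answers. The Early Termination Visit includes a fasting lipid panel (Protocol 6.6). Under Protocol 9.3.1.1 and SAP 11.1, an off-drug sample from that visit is post-baseline and could be carried forward. Under SAP 9.4 and 9.6 it is discarded if taken more than 2 days after the last dose.

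At stake is the size of the headline estimate, which Protocol 1.4 says will feed into Phase 3 planning. The stratum results are more exposed, because they have fewer subjects and no per-protocol check.

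**Working it through.** **Inputs**

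- Test: "2-sided t-test at the 5% level of significance" (Protocol 9.1).
- Effect and power: "A sample size of 26 randomized subjects in the gemcabene 600 mg group and 26 randomized subjects in the placebo group" in each statin stratum "is expected to provide 80% power to detect a difference of 17% in the percent change from baseline to Week 12 in LDL-C" (Protocol 9.1).
- Variability and loss: "a common standard deviation of 20, and a drop-out rate of 10" per cent (Protocol 9.1).
- Allocation: "in a 1:1 ratio to the following treatment groups: placebo or gemcabene 600 mg" (Protocol 3.1), so 52 per arm overall.
- d, the fraction of gemcabene subjects who stop: 10% as planned, with 5% and 20% as a range.
- r, the fraction of the drug effect still present at Week 12 in those who stop: not in the documents; 0, 0.5 and 1 are assumed.

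**Step 1: the plan's own figure.** With a difference of 17 and SD 20, the noncentral t calculation gives 78.7% power at 22 per arm and 80.5% at 23. Then 23 / 0.9 = 25.6, rounded up to 26. The stated 26 per arm per stratum (104 in total) is reproduced.

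**Step 2: size of the overstatement.** Take 17 points as the on-drug effect at every visit.

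- Carrying on-drug values forward estimates 17(1 − d) + 17d = 17.
- The effect in all randomized subjects is 17(1 − d) + 17dr.
- The overstatement is the difference, 17d(1 − r).

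Placebo drop-outs do not enter, because they have no drug effect to carry forward.

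| Gemcabene drop-out | r = 0: effect (overstatement) | r = 0.5 | r = 1 |
|---|---|---|---|
| 5% | 16.15 (0.85) | 16.58 (0.43) | 17 (0) |
| 10% | 15.3 (1.7) | 16.15 (0.85) | 17 (0) |
| 20% | 13.6 (3.4) | 15.3 (1.7) | 17 (0) |

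At r = 0 the relative overstatement is 1.7 / 15.3 = 11% at 10% drop-out and 3.4 / 13.6 = 25% at 20%.

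**Step 3: power for the all-randomized effect.** This assumes r = 0, SD 20 and every randomized subject measured at Week 12.

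| Drop-out | Effect | Per stratum (26 per arm) | Overall (52 per arm) |
|---|---|---|---|
| none | 17 | 85.2% | 99.0% |
| 10% | 15.3 | 77.2% | about 97% |
| 20% | 13.6 | 67.2% | 93.0% |

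**Step 4: would a repeated-measures model remove the gap?** A simulation used 52 per arm, four visits, SD 20, an assumed between-visit correlation of 0.6, a 17-point effect at every visit, drop-out unrelated to outcome, and return to the placebo level after stopping. LOCF and a missing-at-random likelihood-type estimate both gave about 17.0, against all-randomized effects of 15.3 (10% drop-out) and 13.6 (20%). Both use only on-treatment values, so both estimate what would be seen if everyone had stayed on drug. The LOCF 95% interval covered the all-randomized effect 92.8% of the time at 10% and 86.4% at 20%.

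With 20% drop-out on gemcabene and 5% on placebo, LOCF gave 16.92 against 13.53. The overstatement is again about 3.4, so it follows gemcabene drop-out and does not need drop-out to differ between arms.

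**The case against.** The best defence is that an effect while on treatment is a reasonable target for a Phase 2 study. Protocol 1.2 reports clear LDL-C lowering in a 2-week study, so an early on-drug value may be close to the on-drug Week 12 value. That stands, but the plan does not name this target, and its two carry-forward rules do not agree on it.

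The per-protocol repeat is also more than nothing. It removes most carried-forward values and shows whether they drive the result. It cannot show what happens to LDL-C in those who stop.

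Nor is every drop-out credited through LOCF. Subjects with no post-baseline efficacy value are outside the Full Analysis Set. A termination sample after Day 71 and within 2 days of the last dose falls in the Week 12 window and counts as observed. The drop-out rate is therefore an upper bound on the share imputed.

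A reader might also infer that the standard error is too small, since 20 × √(2/52) = 3.92 with drop-outs counted and 20 × √(2/46.8) = 4.13 without. That compares LOCF with a completers-only analysis, not with LOCF's own sampling error. In simulation at 10% drop-out, the model standard error of 3.92 was close to the empirical SD (3.95 and 3.98 in two runs). Rejection under the null was 5.7% in 4,000 runs, close to nominal. The coverage loss in Step 4 comes from a shifted target, so the standard-error criticism is not made here.

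**Conclusion.** The point holds as one about the estimate. Single LOCF is the only method for missing Week 12 LDL-C. SAP 9.4 and 9.6 confine it to on-treatment values and override observed off-drug ones, and no planned analysis tests informative drop-out. At the planned 10% drop-out the overstatement of the all-randomized effect is 1.7 of 17 points under full loss of effect, 0.85 under half retention and nil under full retention. The 1.7 points are under half a standard error (1.7 / 3.92 = 0.43).

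These figures rest on a 17-point on-drug effect and on an assumed r, for which the documents give no value. I took r between 0 and 1. Appendix E of the protocol recommends also stopping the statin when its hepatic discontinuation criteria are met, so a rise above baseline in some subjects is not excluded.

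Severity is moderate to minor. Overall power stays about 97%, while the stratum analyses fall to about 77% under full loss. A reader might infer that the primary test is invalid, or that MMRM alone would cure the problem. Neither the documents nor the checks support either reading.

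**What to change.** 1. Reconcile Protocol 9.3.1.1 and SAP 11.1 with SAP 9.4 and 9.6. State whether the primary estimate is an on-treatment effect or an effect in all randomized subjects, and list any departure from the protocol in SAP Section 8.
2. Keep LDL-C values observed after the last dose (Early Termination or Week 12 samples) and use them in at least one analysis of the primary endpoint.
3. Pre-specify a placebo-based multiple-imputation analysis of Week 12 percent change, overall and within each statin stratum. State how much of the earlier on-drug response the imputation model retains, since that fixes r.
4. MMRM over Weeks 2, 4, 8 and 12 may replace the LOCF ANCOVA for the on-treatment effect. It is optional and does not by itself remove the overstatement.

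The cost is SAP wording and standard programming on samples already scheduled; no visits are added. Off-drug termination samples are not all taken at Week 12, so item 2 informs the question without settling it. The all-randomized estimate will probably be slightly less favourable. The changes should be fixed before unblinding.

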9.3.1.2 Secondary and exploratory efficacy analyses

Secondary efficacy endpoints include:

- Percent change from baseline to Week 12 in LDL-C for each statin intensity stratum (high-intensity; moderate-intensity);
- Change from baseline to Week 2, Week 4, Week 8, and Week 12 in LDL-C;
- Change and percent change from baseline to the average of Week 8 and Week 12 measurements in LDL-C;
- Change and percent change from baseline to Week 12 in LDL-C in subjects on and not on ezetimibe;
- Change and percent change from baseline to Week 2, Week 4, Week 8, and Week 12 in non-HDL-C, TC, TG, HDL-C and VLDL-C;
- Percent of subjects achieving LDL-C reduction of $\geq 10\%$, $\geq 15\%$, and 20% at Week 4, Week 8, and Week 12;
- Percent of subjects achieving an LDL-C value < 100 mg/dL (2.59 mmol/L) at Week 4, Week 8, and Week 12;
- Change and percent change from baseline to Week 4, Week 8 and Week 12 in Apo B, ApoA-I, ApoA-II, ApoA-V, ApoC-II, ApoC-III, ApoE and Lp(a);
- Change and percent change from baseline to Week 4, Week 8 and Week 12 in hsCRP, SAA, adiponectin, and fibrinogen;
- Change from baseline to Week 12 in Framingham Risk score; and

- Change from baseline to Week 12 in NCEP ATP-III Risk.

The exploratory efficacy endpoints include:

- **CI** [REDACTED]
- [REDACTED]
- [REDACTED]

[figure not shown]
Analysis of secondary and exploratory endpoints will not be adjusted for multiplicity. Each of the secondary and exploratory endpoints will be compared to a significance level of 0.05. Given the large number of endpoints, p-values for the secondary and exploratory endpoints will be considered descriptive.

For continuous secondary and exploratory efficacy endpoints related to change/percent change in basic fasting lipids, lipoproteins, hsCRP, SAA, fibrinogen, adiponectin, FPG, fasting insulin and **CI** [REDACTED] the same ANCOVA for the primary efficacy endpoint will be used, with the respective baseline included as the covariate. Note that for secondary endpoints such as change from baseline in LDL-C within the moderate-intensity stratum, the ANCOVA model will not include a term for baseline statin intensity stratum. Baseline for TC, non-HDL-C, HDL-C and VLDL-C are defined similarly to baseline for LDL-C. Baseline for fasting lipoproteins, hsCRP, SAA, fibrinogen, adiponectin, FPG, fasting insulin and serum **CI** [REDACTED] are defined as the value from pre-dose Day 1/Visit T1. Baseline for HbA1c is the value from the first visit (Pre-Screening or Screening Visit).

Each ANCOVA will be performed using the FAS (or the specific subgroup within the FAS that is indicated in the specific endpoint [e.g. subgroup of baseline high-intensity statin subjects]), with subjects included in their randomized treatment group regardless of the treatment they actually received. Missing values for post-randomization time points will be imputed using LOCF; only post-baseline values will be used for the imputation. The output from each ANCOVA will include the LSM and SE for both treatment groups, along with the placebo-corrected LSM, its 95% CI and associated p-value. For every continuous endpoint (each parameter, each time point), if non-normality is detected, then either the data will be transformed so that it is normally distributed or a nonparametric test will be used.

The percent of subjects achieving LDL-C reduction of $\geq 10\%$, $\geq 15\%$ and $\geq 20\%$ at Week 4, Week 8, and Week 12 will each be analyzed using a logistic regression with treatment, baseline statin intensity (high-intensity; moderate-intensity), baseline diabetes (Y/N) and baseline LDL-C value as independent factors. For each analysis, the percent of subjects in each treatment group meeting the criteria, the odds ratios with 95% CI, and p-value will be provided. The percent of subjects achieving a LDL-C value <100 mg/dL (2.59 mmol/L) at Week 4, Week 8, and Week 12 will be analyzed in the same manner, with similar output provided for each endpoint. For all of these endpoints, the FAS will be used, with subjects included in their randomized treatment group regardless of the treatment they actually received.

Framingham Risk scores and estimated 10-year risk will be summarized at baseline and Week 12. Additionally, the change from baseline to Week 12 in Framingham Risk scores and estimated 10-year risk will be summarized. The number and percent of subjects in each NCEP ATP-III Risk category will be summarized at baseline and Week 12. Also, a shift table of NCEP ATP-III Risk categories from baseline and Week 12 will be provided. The FAS, with subjects included in their randomized treatment group regardless of the treatment they actually received, will be used for all of these summarizations. Finally, ^C

Confirmatory analysis of the secondary and exploratory endpoints will be performed using the PPS.

